**2b: Patient's bedside CRF**

**African Critical Illness Outcomes Study (ACIOS) – Patient CRF**

**Clinical assessment**

Date of assessment:

Vital signs done by the investigating team:  Y  N If no, specify  Vital signs from patient records  Not done

Position of patient:

Lying flat on back(<30°)  Lying on side  Head-up(30°-60°)  Sitting(>60°)  Head-down  Other

Airway patency:  Normal  Partial obstruction  Complete obstruction

Conscious level (AVPU):  Alert  Responds to Voice  Responds to Pain  Unresponsive

Heart rate  /min Oxygen saturation  % Respiratory rate  /min

Systolic blood pressure  /mmHg Diastolic blood pressure  /mmHg

Currently receiving IV fluids  Y  N Receiving oxygen (now)  Y  N

Receiving vasopressor/inotrope (now)  Y  N Airway action (now)  Y  N

Circle the worst pain you had in the last 24 hours: 0 (no pain) 1 2 3 4 5 6 7 8 9 10 (worst pain you can imagine)

**Other information**

Date of hospital admission:  d  m  m  y  y  y  y Urgency of admission:  Emergency/acute  Elective

Age  /years Sex  M  F

Ward type:  Medical  Surgical  Maternal  Other

Ward level:  General ward  High care unit/HDU  ICU

Main category for admission:  Non-communicable disease  Maternal health  Trauma  Infection

Known chronic disease or pregnancy (tick all that apply):

Pregnant  Hypertension  Diabetes  Cancer  COPD / Asthma

Heart Disease  HIV / AIDS  Tuberculosis  Other  None

Any surgery during this admission:  Y  N Treatment limitations (e.g. not for resuscitation):  Y  N

**Follow-up**

Total days in hospital from admission to discharge  /

Status at 7th day in-hospital after clinical assessment:  Discharged Alive  Alive still in-hospital  Died

Date of discharge or death  d  d  m  m  y  y  y  y

ACIOS unique patient ID  / / / /

-----  
Patient name: \_\_\_\_\_

DOB  d  d  m  m  y  y  y  y

Patient hospital number \_\_\_\_\_

Ward \_\_\_\_\_ Bed \_\_\_\_\_

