#### 5.5 Secondary outcomes

- Provision of essential emergency and critical care
- Length of hospital stay

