#### **7.3.3 Patient level data collection**

On the specified day of data collection, every patient fulfilling the inclusion criteria in every department and ward in the hospital will be included in the study. Patients who are absent from their beds when the study team arrive, (for example, are in an operating theatre, or undergoing a medical investigation), will be re-visited later the same day and included when they are back in their bed, or when they are in a bed where inclusion is possible such as in a surgical recovery room. Data on patient demographics, medical information and current care provided will be collected from the patient and from the clinical team. The patient's vital sign measurements, (respiratory rate, oxygen saturation, blood pressure, heart rate, conscious level), will be checked by the study team using the hospital's equipment. If it is inappropriate for a patient's vital signs to be checked – for example if the clinical team has made the decision to refrain from vital sign observations as the patient is in the final stage of dying, (may be termed 'on an end-of-life pathway', "moribund", 'gasping' or 'late palliative phase' by the clinical team), or if the patient refuses permission to measure their vital signs – then the patient will be included in the study but vital signs will not be measured. It will be acceptable for the study team to record the last vital signs recorded in the patient's file for these patients. For women in active labour, the vital signs will be measured between contractions. Detailed data collection procedures will be described in the study's Standard Operating Procedures. Data will be collected by clinician investigators, and/ or clinician researchers working at the site.

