### 8. Definitions

*Critical illness (co-primary outcome):* a state of ill health with vital organ dysfunction, a high risk of imminent death if care is not provided and the potential for reversibility. Patients will be classified as critically ill if they have one or more severely deranged vital signs as in Figure 1. The cut-offs are those used in the Critical Illness and Sepsis Prevalence and Outcomes Study (CRISPOS) study and based on previous research in Tanzania and Sweden :

Criterion	Vital signs	Definition critically ill
Conscious level	Conscious level (AVPU Scale)	P or U
Respiratory	Respiratory rate per minute	<8 or >30
	Oxygen saturation (%)	<90
Circulatory	Heart rate per minute	<40 or >130
	Systolic blood pressure (mmHg)	<90

Figure 1: Criteria for the definition of critical illness

*Hospital population:* all adult patients aged 18 years or over who have been admitted for inpatient care in any department or ward in participating hospitals on the day of data collection.

*Essential Emergency and Critical Care (EECC):* the care that all critically ill patients should receive, in all hospitals in the world including clinical processes such as oxygen therapy, intravenous fluids and patient positioning to protect the airway, as described in the 2021 global consensus.

*Availability of resources for EECC:* The 66 resources necessary for the provision of EECC including items such as pulse oximeters, oxygen masks and intravenous fluids.

*Coverage of EECC:* The proportion of critically ill patients receiving EECC.

Patients will be deemed to be receiving EECC if they are:

- critically ill due to the conscious level criterion (Figure 1) **and**:
  - are lying in the lateral position **or**

- have an oro-pharyngeal or naso-pharyngeal airway inserted in their pharynx **or**
- have an ongoing chin-life or jaw-thrust **or**
- have other airway protection
- critically ill due to a respiratory criterion (Figure 1) **and**:
  - are receiving oxygen
- critically ill due to a circulatory criterion (Figure 1) **and**:
  - are receiving intravenous fluids **or**
  - are receiving a vasopressor or inotrope

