*Acute Hospital:* A hospital admitting acutely unwell patients – i.e. patients who have a recent onset or exacerbation of a somatic condition and require timely care. Acute hospitals can be owned and run by the government or by a private or other organisation. Hospitals that only admit chronically unwell patients, or only patients for rehabilitation, or only patients for elective surgery are not regarded as acute hospitals and are not eligible for participation in ACIOS. Hospitals, units and wards exclusively for patients with psychiatric conditions are not regarded as acute hospitals.

*In-hospital mortality (co-primary outcome):* Death in-hospital. Patients discharged alive are not followed-up at home.

*1-day and 7-day outcomes:* The defined time for the outcomes is from the point of inclusion of the patient into the study to hospital discharge or death, censored at 7-days.

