### 10.2 Statistical analysis

An ACIOS statistical analysis plan (SAP) will be written prior to inspection of the final dataset. Data will be presented at a continental African level. All institutional and national level data will be anonymised prior to publication. Categorical variables will be described as proportions and will be compared using

chi-square tests. Continuous variables will be described as mean and standard deviation if normally distributed, or median and inter-quartile range if not normally distributed. Comparisons of continuous variables between groups will be performed using t-tests, one-way ANOVA or equivalent non-parametric tests as appropriate. Univariate and hierarchical, multivariable, multi-level logistic regression models will be constructed to determine the relationship between the presence of critical illness and mortality and the relationship between essential emergency and critical care provision and mortality.

Results of logistic regression will be reported with 95% confidence intervals. The models will be assessed with predefined sensitivity analyses to explore possible interacting factors and examine any effect on the results. A single final analysis is planned at the end of the study.

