**Main category for admission:** The main diagnosis or reason that the patient is being treated in hospital.

**Treatment limitations:** A patient has a treatment limitation if the clinical team have made the clinical judgement that some treatments would not be in the patient's best interest. For example "DNR" (do not resuscitate in the event of a cardiac arrest), or "Not for ICU" in the event of deterioration.

**Days in hospital:** Total number of days in hospital from admission.

**Status at hospital discharge or 7th day in-hospital after clinical assessment:** The survival status of the patient at hospital discharge, or at the 7th day after clinical assessment (if the patient had not yet been discharged). The study is censored at the 7th day after clinical assessment.

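### Length of stay is counted from admission in a one-day census of inpatients, so the planned mean or median describes patients in a bed that day and generally overstates the stay of admitted patients

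*Protocol*

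**What the plan says.** - **Outcome.** Protocol 5.5 names "Length of hospital stay" and gives no time origin, end point or target population. No objective (5.2) or research question (5.3) mentions it.
- **Sampling.** Section 7.3.3 enrols "On the specified day of data collection, every patient fulfilling the inclusion criteria in every department and ward in the hospital". Section 8 defines the hospital population as adults admitted to "any department or ward in participating hospitals on the day of data collection".
- **Clock on the CRF.** The follow-up part of the patient CRF (Appendix 2b) asks for "Total days in hospital from admission to discharge". Its definitions page explains days in hospital as "Total number of days in hospital from admission". Neither says what to enter for a patient still in hospital at day 7.
- **Clock in section 8.** Under the label "1-day and 7-day outcomes", the protocol states: "The defined time for the outcomes is from the point of inclusion of the patient into the study to hospital discharge or death". Follow-up on this clock stops at day 7. Length of stay is not named there.
- **Analysis.** Section 10.2 describes continuous variables by mean and standard deviation, or by "median and inter-quartile range if not normally distributed", with simple tests between groups. Neither document mentions length-biased sampling, left truncation or delayed entry.
- **SAP.** The supplied SAP covers the pain sub-study and does not analyse length of stay.

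**The concern.** A patient whose stay lasts 20 days is in a bed on ten times as many days as one whose stay lasts 2 days (20/2 = 10), and is ten times as likely to be caught by a single-day census. Quick discharges and early deaths are largely missed. Because the CRF counts back to admission, the over-sampled time before the study day is part of the recorded value. More hospitals or more patients would narrow the confidence interval around the same shifted figure.

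With no target population stated, a result headed length of hospital stay will be read in the ordinary sense, as how long an admitted patient stays. A raw group contrast is exposed too, because the distortion depends on how variable stays are within each group.

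**Working it through.** **Inputs.** Sampling scheme: 7.3.3 and section 8. Origin at admission: patient CRF and its definitions. Cut-off 7 days after assessment: 7.3.4 and the CRF definitions. The documents give no length-of-stay figure, so there is nothing of theirs to reproduce. The mean and CV (SD/mean) of stay are assumptions: means of 4 to 14 days, CV 0.5 to 1.5, gamma and lognormal shapes, steady census.

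**Step 1: complete stays.** If X is the stay among admissions with mean μ, the stay of patients found in a bed has mean E[X²]/μ = μ(1 + CV²). The ratio is 1 + 0.71² = 1.50 at CV 0.71, 2.00 at CV 1.0 and 1 + 1.41² = 2.99 at CV 1.41.

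**Step 2: apply the day-7 cut-off.** Recorded stay = A + min(B, 7), with A the time already spent in hospital and B the time remaining. For exponential stays (CV 1.0), A and B each have mean μ, so the ratio is [μ + μ(1 − e^(−7/μ))]/μ:
- μ = 4: (4 + 3.30)/4 = 1.83
- μ = 7: (7 + 4.42)/7 = 1.63
- μ = 10: (10 + 5.03)/10 = 1.50
- μ = 14: (14 + 5.51)/14 = 1.39

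Simulation (1,000,000 draws per scenario) agrees and extends this to other CVs. Ratio of the recorded mean to the mean among admissions, across the two shapes:

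| Mean stay, days | CV 0.5 | CV 0.71 | CV 1.0 | CV 1.41 |
|---|---|---|---|---|
| 4 | 1.2 | 1.4 | 1.8 | 2.4–2.5 |
| 7 | 1.2 | 1.3 | 1.6 | 2.1–2.2 |
| 10 | 1.1 | 1.2 | 1.5 | 2.0 |
| 14 | 1.0 | 1.1 | 1.4 | 1.9 |

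Taking CV up to 1.5 moves the top corner (mean 4 days) only to about 2.5 (lognormal) or 2.6 (gamma). Medians depend more on shape: their ratio ran from about 1.1 to 4.6 for CV 0.71 to 1.41.

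**Step 3: does dropping open stays help?** Only partly. Among patients discharged within 7 days, the mean ratio is still about 1.05 to 2.1 for CV 0.71 to 1.41.

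**Step 4: does delayed entry recover the admission figure?** Mean stay 6 days, about 30,000 census patients, 7-day follow-up, no deaths simulated:

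| Stay distribution | Median, admissions | Median, census (full stays) | Median, delayed entry |
|---|---|---|---|
| Exponential | 4.2 | 10.0 | 4.25 |
| Lognormal, CV 0.7 | 4.9 | 7.3 | 5.0 |
| Lognormal, CV 1.0 | 4.2 | 8.5 | 4.5 |
| Lognormal, CV 1.5 | 3.3 | 10.9 | 3.5 |

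The estimate is within about 0.3 day of the truth. This tests the handling of truncation and censoring, not the competing-risk part.

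**Step 5: group comparisons.**
- *Raw summaries, groups fixed at admission.* With lognormal stays of mean 7 days (CV 0.5) in one group and mean 6 days (CV 1.2) in the other, medians among admissions are 6.3 and 3.8. In the census with the day-7 cut they are about 7.6 and 8.3, so the order reverses.
- *Delayed entry, groups defined on the study day.* Give everyone the same exponential stay (true median 4.2 days) and let 20% be critically ill only in their last 2 days. Delayed entry then gives medians of about 1.25 days for the critically ill and 4.75 for the rest: a gap created by the grouping alone.

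**The case against.** **The target may be inpatients on the study day.** Section 8 defines the hospital population that way, and for that population the census is the right sample. The protocol nowhere says it will present stay as that of admitted patients, so a reader who infers that the planned summary is simply wrong goes too far. What remains is that 5.5 states no target, so the figure needs a label at the least.

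**The size depends on assumptions.** A reader might take 1 + CV² and quote inflation of 1.5 to 3 times. That applies to complete stays, and the protocol stops follow-up at day 7. With the cut-off the supported range is lower, and it reaches about 1.0 at a low CV with long stays.

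**Two conflicting origins?** A reader might infer that section 8 contradicts the CRF. Its clock is labelled for the 1-day and 7-day outcomes, follows directly after in-hospital mortality and does not name length of stay. The only text defining days in hospital starts at admission. This is an ambiguity, not a contradiction.

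**Delayed entry does not repair the critical-illness comparison.** This stands. Critical illness is measured once, on the study day, so it is not a baseline characteristic on an admission clock; step 5 shows the damage. Section 10.2 also specifies no length-of-stay comparison beyond its generic wording on continuous variables.

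**The main analysis plan is not supplied.** Section 10.2 defers detail to an ACIOS SAP, and the one in hand is for the sub-study. Whether the main plan handles this cannot be checked, so the point rests on the protocol as written.

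**Conclusion.** The concern holds for the overall summary of this secondary outcome. Followed as written, the plan gives the stay of patients present on the study day. Read as the stay of admitted patients, the mean is about 1.1 to 2.5 times too high for assumed mean stays of 4 to 14 days and CV of about 0.7 to 1.5, and close to right at CV 0.5 with a 14-day mean. These figures assume a steady census and that stays open at day 7 are counted up to day 7, which the plan does not state. The true CV and mean are unknown. The documents do not support a fixed factor of 1.5 to 3, two contradictory definitions, or the idea that one estimator would also rescue a comparison by critical illness. The point is confined to length of stay and is worth correcting because the remedy is cheap.

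**What to change.** In sections 5.5, 8 and 10.2 of the protocol, and in the main analysis plan:

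1. Define length of stay from the date of admission, and state that the section 8 clock starting at inclusion does not apply to it.
2. Label any plain mean or median *stay of patients present on the study day*, and say how stays open at day 7 and stays ended by death are counted.
3. For the overall stay of admitted patients, use a delayed-entry (left-truncated) estimate: clock from admission, entry to the risk set on the assessment date, live discharge as the event, death as a competing event, censoring 7 days after assessment.
4. Do not use that estimator to compare critically ill with other patients. Present any such comparison as time from assessment onward, or as descriptive only.

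**Cost.** Wording changes and one standard estimator. Admission date, assessment date, day-7 status and date of discharge or death are already on the CRF, so no new data are needed. The early part of the curve will rest on patients admitted on or just before the study day and will be less precise. The estimator does not need a steady admission pattern, but it assumes that stay is independent of admission date.

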## Definitions:

**Position of patient:** The position the patient is in the bed/chair when the investigating team arrive at the bedside. The number of degrees refers to the angle of the head and body compared to the legs.

**Airway patency:** Normal is an unobstructed airway. Partial obstruction may be indicated by stridor, secretions in the airway identified by gurgling, or snoring. Complete obstruction is evident by a see-saw chest movement (chest down and abdomen up with attempted breathing against a closed glottis). Complete obstruction is an airway emergency and requires calling the attending clinical team immediately.

**Conscious level AVPU:** Measurement of conscious level. Is the patient Alert = A. If they are not alert but they respond to your voice = V. If they don't respond to voice but respond to a painful stimulus = P. If they remain unresponsive even with a painful stimulus = U (unresponsive).

**Currently receiving IV fluids:** At the time of clinical assessment, the patient is receiving IV fluids if IV fluids are hanging at the bedside, and currently dripping into an intravenous cannula, or the patient has been receiving fluids as described within the previous few minutes but is now finished and a new fluid is being prepared to be administered.

**Receiving oxygen (now):** At the time of clinical assessment, the patient is receiving oxygen if supplementary oxygen is currently flowing into a nasal cannula, face mask or other delivery device that is correctly fitted so that oxygen is entering the patient's lungs.

**Receiving vasopressor/inotrope (now):** Ongoing care with a vasopressor or inotrope infusion – for example noradrenaline, adrenaline, dopamine or dobutamine.

**Airway action (now):** An action to open the airway or maintain a free airway. For example: chin lift, jaw thrust, oro-pharyngeal airway, naso-pharyngeal airway, intubated patient.

**High care unit/HDU:** A unit or ward or part of a ward which is dedicated to providing an increased level of care when compared to a general ward. High care units often have increased nurse:patient ratios, more equipment and more advanced care such as oxygen, CPAP, vasopressors etc. This does *not* include units with mechanical ventilation, as that is an ICU. Includes recovery rooms providing an increased level of care.

**ICU:** A unit or ward which is dedicated to providing an increased level of care when compared to a general ward or high care unit including mechanical ventilation.

**Main category for admission:** The main diagnosis or reason that the patient is being treated in hospital.

**Treatment limitations:** A patient has a treatment limitation if the clinical team have made the clinical judgement that some treatments would not be in the patient's best interest. For example "DNR" (do not resuscitate in the event of a cardiac arrest), or "Not for ICU" in the event of deterioration.

**Days in hospital:** Total number of days in hospital from admission.

**Status at hospital discharge or 7th day in-hospital after clinical assessment:** The survival status of the patient at hospital discharge, or at the 7th day after clinical assessment (if the patient had not yet been discharged). The study is censored at the 7th day after clinical assessment.

## Guidance for use of paper case record form (CRF)

1. **Investigators should write the patient's name and date of birth on the bottom of the CRF. When you enter the data on the internet based CRF you will receive an ACIOS patient ID. Please write this on the paper CRF as well in case we need to contact you to check your data.**
2. **The clinical assessment and the patient's vital signs MUST be completed at the same time by the investigating team. Only in exceptional circumstances can the vital signs data be taken from the medical records.**
3. **Please take care to enter the date clearly and correctly. Mistakes are common data describing time and date.**

The African Critical Illness Outcomes Study (ACIOS)

A prospective, multi-country, multi-centre, observational study to determine the hospital point-prevalence and mortality rates of adult patients with critical illness in acute hospitals in Africa.

Sub-study: Severity of pain in hospitalised patients in Africa

[figure not shown]
Statistical Analysis Plan (SAP)

Version 1.0

Date: 08/04/2024

Registration ClinicalTrials.gov - NCT06051526

Based on “ACIOS protocol version 2.0 HREC approved”

Persons contributing to the analysis plan	
Names and positions	Assoc [name], MUHAS [name], UCT [name], QMUL [name] [name], KI [name] (Statistician) [name], UCT Assoc [name] [name], UCT [name], UCT
Authorisation	
Position	Chief Investigator
Name	Assoc [name], MUHAS
Signature	
Date	8 th April 2024
Position	Trial Statistician
Name	[name]
Signature	
Date	8 th April 2024

Remit of the SAP

The purpose of this document is to provide details of the statistical analyses and presentation of results to be reported within the sub-study – “Severity of pain in hospitalised patients” – of the ACIOS study. It is important to set these out and to agree them in advance of inspecting the outcome data for the study, so that data derived decisions in the analysis are avoided. Any exploratory, post hoc, or unplanned analysis will be clearly identified as such in the study analysis report.

Timing of the SAP

The SAP version 1.0 was written prior to the investigators having access to the data.

1. Study Summary

Short title	ACIOS – pain severity
Methodology	A prospective, international, multi-centre, observational study.
Research sites	Acute hospitals in African countries.
Objective	To determine the severity of self-reported pain in hospitalised patients across Africa.
Number of patients	Not specified. All eligible patients in participating hospitals.
Inclusion criteria	All in-hospital patients aged 18 years or older in all departments and wards in participating hospitals in Africa.
Exclusion criteria	None
Patient follow-up	Until hospital discharge or death, censored at 7 days after inclusion.
Primary outcomes	
 1. To determine patients’ self-reported severity of pain in the preceding 24 hours on a scale of 0 – 10. 2. To determine the association between severity of pain and critical illness in adult patients admitted to hospitals across Africa. 3. To determine the association between severity of pain and mortality in adult patients admitted to hospitals across Africa.
Data collection duration	One day in each hospital in September-December 2023 plus 7 days follow-up in each hospital
Proposed start date	7 th September 2023
Proposed end date	27 th December 2023

Introduction

Pain is poorly managed in hospitalised patients (Wu and Raja 2011). Uncontrolled pain in hospitalised patients is strongly associated with both short- and long-term complications. Patients are more likely to develop secondary complications such as sepsis, bleeding, and infarctions if their pain is not adequately managed (Brennan, Carr et al. 2007, van Boekel, Warlé et al. 2019). Further, pain of >7 on a visual analogue scale is strongly associated with an increased risk of persistent pain (Sinatra 2010). In high-income countries, up to 86% of hospitalised patients report having poorly managed pain (Wu and Raja 2011, Gan 2017). However, there is a paucity of the literature on the severity of acute pain in hospitalised patients in Africa. Therefore, this sub-study aims to determine the severity of self-reported pain in hospitalised patients across Africa; and the relationship between severity of pain and (1) critical illness and (2) mortality. This study falls under the ACIOS – African Critical Illness Outcome Study – parent study.

2. Statistical Analysis Plan

